2.6 Analysis of the key secondary objective

2.6.1 Key secondary variable

The key secondary variable is the proportion of all randomized subjects who achieve PASI 90 at Week 104. In order to reduce selection bias, all subjects who do not achieve PASI 90 at Week 52 will also be included in the analysis at Week 104 using the PASI improvement obtained at Week 104 only.

A subject who fails to achieve PASI 90 response at Week 104, irrespective of the responses over the past visits will be considered non-responder. Similarly, subjects who achieved PASI 90 response at Week 104, but not at any of the past visits will be considered responder.

This would mean that if a subject achieves PASI 85 (85% improvement in PASI score compared to Baseline) at Week 52, and the improvement in PASI increases to 90% at Week 104, the subject will be considered responder in the analysis at Week 104.

2.6.2 Statistical hypothesis, model, and method of analysis

For the key secondary analysis, the following hypothesis testing will be performed:

$$H_{02}: p_{sec}^* = p_{nbUVB}^* \text{ versus } H_{A2}: p_{sec}^* > p_{nbUVB}^*$$

where p_{sec}^* and p_{nbUVB}^* are the proportion of subjects who achieve PASI 90 response at Week 104 in the secukinumab 300 mg s.c. (Arm A1) and nb-UVB (Arm B1) arms respectively. This testing will be performed using an exact logistic regression analysis similar to the primary analysis, with the strategy below under consideration. In case of no covariates is significant, exact logistic regression analysis will be performed using only Treatment as fixed effect factor.

Missing data will be handled similarly as for the primary endpoint analysis. Subjects who relapse will be considered non-responders in addition to those who discontinue the study before Week 104 because of lack of efficacy or AEs.

Testing strategy

Since the primary and the key secondary hypotheses are not mutually independent, an adjustment for multiplicity is considered here to control the alpha level (Type I error) i.e., familywise error rate.

This adjustment will be made using a hierarchical testing procedure which states that first H_{01} will be tested at 1-sided $\alpha=2.5\%$ level of significance. The obtained p-value from the fitted logistic regression model will be divided by 2 and this resultant p-value needs to be considered. If the resultant p-value is smaller than 0.025, H_{01} is rejected at 2.5% significance level, concluding that there is strong evidence to consider that secukinumab is performing better than nb-UVB at Week 52. However, if this resultant p-value is greater than 0.025, H_{01} is not rejected at 2.5% significance level, concluding that the evidence obtained from the observed sample is not strong enough to say that any one of the treatment arms is performing better than the other. "PASI score" eCRF page will be used to get above information.

The testing sequence will continue to test H_{02} at $\alpha=2.5\%$ (1-sided), only if H_{01} is rejected.

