2.3.2.1 Demographics

Continuous demographic variables captured either at Screening or at Baseline include:

- age (in years; calculated in the eCRF from date of birth and Visit 1 date)
- height at Screening (in centimeters)
- weight at Baseline (in kilograms)
- body mass index (BMI, in kg/m²) = (body weight at Baseline in kilograms) / (height at Screening in centimeters/100)²

For BMI, height and body weight used is the last value prior to randomization. If there is no weight recorded prior to taking of study drug, BMI will be missing.

Categorical demographic variables captured either at Screening or at Baseline include:

- age categories (18-30, 31-50)
- gender (male, female)
- race (Caucasian, Black, Asian, Native American, Pacific Islander, Unknown, Other)
- ethnicity (Hispanic or Latino, East Asian, Southeast Asian, South Asian, West Asian, Russian, Mixed, Not Reported, Unknown, Other)
- child-bearing potential (able to bear child, premenarche, post-menopausal, sterile - of child bearing age)
- skin type (I, II, III, IV, V, VI)
- smoking status at Baseline (never, current, former)
 - estimated number of pack-years (The estimated number of pack years is defined as the total years of smoking multiplied by cigarette packs smoked per day (e.g. 10 pack years = 1 pack /day x 10 yrs., or ½ pack/day x 20 yrs.). The number of pack years will be analyzed as recorded on the eCRF.)
 - Time since last date of tobacco use (for former category) = (Date of Visit 1 – Date of last use of tobacco + 1)/365.25.
- Presence of cardiovascular history (Yes/No)

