2.5.2 Statistical hypothesis, model, and method of analysis

For the primary analysis, the following hypothesis testing will be performed:

$$H_{01}: p_{sec} = p_{nbUVB} \text{ versus } H_{A1}: p_{sec} > p_{nbUVB}$$

where p_{sec} and p_{nbUVB} are the proportion of PASI 90 responders in the secukinumab 300 mg s.c. (Arm A1) and nb-UVB (Arm B1) groups, respectively.

The primary analysis method for PASI 90 response at Week 52 will use a logistic regression model with treatment as an explanatory variable and significant covariates among Baseline PASI score, age, and BMI. The best subset of the significant covariates will be selected using a forward selection method based on the likelihood ratio test. Interaction terms with treatment will also be considered, if significant, among the best subset of selected covariates and the treatment term.

Statistical significance will be evaluated at a 1-sided alpha level of 0.025. The estimated adjusted odds ratio for Arm A1 versus Arm B1 will be displayed along with the associated 2-sided 95% confidence interval (equivalent to the 1-sided 97.5% confidence interval) and p-value.

If there are issues related to the convergence of the logistic regression model, the above hypothesis will be tested using a 1- sided Wald test.

The primary analysis is not expected to be influenced by the use of topical treatment within the first 4 weeks since, any effect will be worn off by Week 52.

The detailed testing strategy including the primary endpoint analysis is provided in Section [2.6.2](#)

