2.5.4 Supportive analyses

Sensitivity analysis will be performed on the primary analysis method for PASI 90 response at Week 52 by repeating the logistic regression model with treatment as an explanatory variable and all three covariates Baseline PASI score, age, and BMI. Interaction terms with treatment also will be considered.

If logistic regression model does not converge the following steps will be performed:

1. Run the PROC GENMOD procedure with EXACT statement;
2. If convergence not reached, remove the covariates from the model one by one until convergence is reached; start with continuous covariates (i.e., baseline BMI by replacing with BMI stratum (< 25, 25-< 30, >= 30), and then baselines PASI score), followed by removing categorical covariates (i.e., BMI stratum etc.);
3. If convergence not reached, perform 1 sided Wald test.

It should be noted that this model might not converge if response rates are too low.

The impact of missing data on the analysis results of PASI 90 at Week 52 will be assessed as well by repeating the logistic regression model using different ways to handle missing data.

- Non-responder imputation
- Tipping point analysis
- Last observation carry forward (LOCF)

A non-responder imputation will be used as a supportive analysis of the primary variable using logistic regression (forward selection method) as described in primary analysis method. In this analysis, a missing value of PASI 90 response at Week 52 will be imputed with non - response regardless of the reason for missing data (e.g., premature study discontinuation, missed visit, administrative issues).

Assuming significance is shown for the primary analysis using non-responder imputation, the tipping point analysis will investigate if, and at which point, significance is not achieved anymore as subjects imputed as non-responders are increasingly reclassified as responders independently for each treatment group.

For PASI 90 response, missing values will be replaced by LOCF. Baseline values will not be carried forward. Similar analysis will be performed using logistic regression (forward selection method) as described in primary analysis method.

An additional analysis might be considered including Week 52 assessments performed later than per visit windowing due to covid.

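### The exact logistic regression for H02 can condition on BMI with no stated rounding, and if unrounded BMI is selected the key secondary test can lose essentially all power or fail to compute

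*SAP*

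**What the plan says.** SAP 2.6.2, with the same sentence in Protocol 9.5.1, defines the H02 test: "This testing will be performed using an exact logistic regression analysis similar to the primary analysis". The primary analysis in SAP 2.5.2 is a "logistic regression model with treatment as an explanatory variable and significant covariates among Baseline PASI score, age, and BMI", and its selection rule is: "The best subset of the significant covariates will be selected using a forward selection method based on the likelihood ratio test". No entry level is stated.

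SAP 2.6.2 simplifies the exact model in one case: "In case of no covariates is significant, exact logistic regression analysis will be performed using only Treatment as fixed effect factor". It does not mention the case where BMI is selected.

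SAP 2.3.2.1 defines BMI as "body weight at Baseline in kilograms) / (height at Screening in centimeters/100)²", with no rounding rule in either direction. Protocol 6.5.3 has weight measured to 0.1 kg and height in centimetres. BMI categories (<25, 25-<30, ≥30) appear in SAP 2.2.1 for subgroups. They appear again in SAP 2.5.4 as a convergence step for the Week 52 sensitivity model, but not in the H02 text. Protocol 9.9 bases the power of H02, around 89%, on an unadjusted Fisher's exact test.

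**The concern.** Exact logistic regression removes a nuisance covariate by conditioning on its sufficient statistic. For BMI that is the sum of BMI over the responders. The test then compares the observed number of Arm A1 responders only with responder sets that have the same total count and the same BMI sum. A ratio of weight to squared height takes a nearly unique value for each patient, so very few other sets may match exactly. With few matching sets the smallest attainable p-value is large, however strong the treatment effect.

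H02 is the only hypothesis after H01 in the hierarchical procedure, and it addresses response a year after secukinumab stops. A real BMI effect is the reason to adjust, and it is also what would bring BMI into the model. The issue arises in a single complete data set. How exact results are pooled over imputations is a separate question.

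**Working it through.** **The plan's own power.** Protocol 9.9 assumes 23% and 5% responders, with 7% and 16% dropout counted as non-response:

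- Arm A1: 23% × (1 − 0.07) = 21.4%, stated as 21%, about 17 of 80.
- Arm B1: 5% × (1 − 0.16) = 4.2%, stated as 4%, about 3 of 80.

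Enumerating both binomials, Fisher's exact test at one-sided 0.025 with 80 per arm has power 90.0%, against a stated figure of around 89%. At 17/80 versus 3/80 its one-sided p is 0.00066.

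**Form of the conditional p-value.** Let C(t) be the number of responder sets with 20 responders, the observed BMI sum and t members in Arm A1. At the null odds ratio, p = Σ C(t) for t ≥ 17, divided by Σ C(t) over all t. The observed set always counts, so p ≥ 1/(number of sets). A p of 0.025 needs at least 40 sets (1/40 = 0.025).

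**Unrounded BMI at trial size.** Trials of 160 patients with 17 versus 3 responders were simulated and their sets counted in exact rational arithmetic. Assumptions: 60% men; heights normal with mean 178 and SD 7 cm (men) or mean 165 and SD 6.5 cm (women), rounded to 1 cm; BMI gamma with mean 27 and SD 5.4; responders drawn at random within arm.

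| Weight recorded to | Enumerated (not enumerable) | Single set | Arm A1 count fixed, p = 1 | Largest set | Smallest p | Trials with p ≤ 0.025 |
|---|---|---|---|---|---|---|
| 0.1 kg (Protocol 6.5.3) | 124 (51) | 80% | 85% | 4 | 0.33 | 0 |
| 0.5 kg | 131 (61) | 37% | 52% | 28 | 0.071 | 0 |
| 1 kg | 104 (50) | 12% | 23% | 32 | 0.037 | 0 |

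The coarser rows cover sites that record weight less finely than the Protocol asks. About 30% of simulated trials were too large to enumerate (51/175, 61/192 and 50/154), and nothing is claimed about those.

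**Rounded BMI and the other covariates.** With BMI rounded to 0, 1, 2 or 3 decimals, the reference set holds about 10²⁰ to 2 × 10²³ sets and p is 0.0005 to 0.0007, close to Fisher. Age in whole years and PASI on its 0.1 grid (which follows from the formula in Protocol 6.4.1) leave 6 × 10²¹ to 10²³ sets and p of 0.0004 to 0.0009.

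**Finite precision.** There are C(160,20) = 1.4 × 10²⁵ possible responder sets. With a BMI SD of 5, the sum over 20 responders has SD 5 × √(20 × 140/159) ≈ 21, so its density at the centre is about 0.399/21 = 0.019. A tolerance of ±10⁻⁸ then admits about 1.4 × 10²⁵ × 0.019 × 2 × 10⁻⁸ ≈ 5 × 10¹⁵ sets; ±10⁻¹³ admits about 5 × 10¹⁰. That is not a single point, but the work is very large and the fit may not complete. With only 5 responders, ±10⁻⁸ admits fewer than one additional set.

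**Overall power.** BMI entry is assumed at a two-sided 5% level. With 20 responders in 160, the information per SD of BMI is 160 × 0.125 × 0.875 × 0.97 = 17.0 (0.97 is an assumed allowance), so the SE is 0.243. If the test never rejects once BMI is in, power ≈ 0.90 × (1 − P(entry)):

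| Assumed log odds ratio per SD of BMI | P(entry) | Overall power |
|---|---|---|
| 0 | 5% | 0.90 × 0.95 = 0.855 |
| 0.2 | 13% | 0.90 × 0.87 = 0.78 |
| 0.4 | 38% | 0.90 × 0.62 = 0.56 |
| 0.6 | 70% | 0.90 × 0.30 = 0.27 |

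**The case against.** The strongest reply is that the SAP never says BMI enters unrounded. Three decimals are enough to restore the test, so the problem may never arise in practice. That stands: the finding is conditional on a data-handling choice the plan leaves open. It still matters, because a confirmatory result should not depend on how many decimals a dataset happens to carry or how software compares sums.

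A second reply is that the H02 code may settle this. SAP 5.6.2 on the key secondary analysis is in the contents list, but its text is not in the document available for review. That also stands, so no claim is made that the plan as a whole lacks a remedy, only that SAP 2.6.2 states none.

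A third reply is that H02 follows the primary analysis, which falls back on a one-sided Wald test if the model does not converge. This might be read across to a fit that fails to compute. A degenerate conditional distribution, however, is a valid exact result and need not be reported as non-convergence, and SAP 2.6.2 does not carry the fallback over explicitly.

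A reader might infer more than the documents support:

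- That p equals 1 whatever the data. Patients of equal height can produce ties that leave several sets; p fell as low as 0.037 with whole-kilogram weights.
- That H02 has zero power. The treatment-only exact test applies when no covariate is selected, and the outcome when BMI is selected depends on rounding and precision.
- That continuous covariates in general are unsuitable here. Age in whole years and PASI on a 0.1 grid behave normally.
- That the order of steps in SAP 2.5.4 is part of the problem. Those steps belong to a Week 52 sensitivity model and do not govern H02.

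**Conclusion.** The concern holds in a conditional form. As written, SAP 2.6.2 and Protocol 9.5.1 allow BMI into the exact H02 model without a precision or categories, and SAP 2.6.2 has no rule for a degenerate or non-computable conditional distribution. If BMI is selected and used unrounded, the test in exact arithmetic has almost no ability to reject: no enumerated trial reached 0.025 at the planned 17 versus 3 responders. With a numerical tolerance at about 20 responders, failure to compute is the alternative outcome; the documents do not determine which would occur.

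The overall loss depends on how often BMI is selected. It is modest if BMI has no effect (0.90 to 0.855) and serious at 38% entry (0.56). The entry level, the BMI effects and the simulated body-size distributions are assumptions, and the power figures further assume that the test never rejects once BMI is in the model. This is more than a missing detail, because following the stated rule literally can defeat the trial's key secondary test.

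**What to change.** In SAP 2.6.2, state that BMI enters the exact H02 model only as the strata already in SAP 2.2.1 and 2.5.4 (<25, 25-<30, ≥30), or rounded to a stated number of decimals. Add that if the conditional distribution is degenerate or cannot be computed, the exact test with treatment as the only term decides H02. That test is equivalent to Fisher's exact test, the basis of the stated 89% power. A simpler alternative is to make the treatment-only exact test the H02 decision outright and report the adjusted exact analysis as supportive.

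SAP 2.15 shows that the Week 104 main-study analysis has already been run. The first step is therefore to document in the study report which form of BMI and which fallback, if any, were used. The text should be corrected to match, not used to choose a test after the results are known.

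The cost is a few lines of text and, at most, a slight loss of covariate precision.

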9.4.2 Statistical model, hypothesis, and method of analysis

For the primary analysis, the following hypothesis testing will be performed:

$$H_{01}: p_{sec} = p_{nbUVB} \text{ versus } H_{A1}: p_{sec} > p_{nbUVB}$$

where p_{sec} and p_{nbUVB} are the proportion of PASI 90 responders in the secukinumab 300 mg s.c. (Arm A1) and nb-UVB (Arm B1) groups, respectively.

The primary analysis method for PASI 90 response at Week 52 will use a logistic regression model with treatment as an explanatory variable and significant covariates among baseline PASI score, age, and body mass index. The best subset of the significant covariates will be selected using a forward selection method based on the likelihood ratio test. Interaction terms will also be considered, if significant, among the best subset of selected covariates and the treatment term.

Statistical significance will be evaluated at a 1-sided alpha level of 0.025. The estimated adjusted odds ratio for Arm A1 versus Arm B1 will be displayed along with the associated 2-sided 95% confidence interval (equivalent to the 1-sided 97.5% confidence interval) and p-value.

If there are issues related to the convergence of the logistic regression model, the above hypothesis will be tested using a Wald test.

The primary analysis is not expected to be influenced by the use of topical treatment within the first 4 weeks since, any effect will be worn off by Week 52.

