2.1 Data analysis general information

Data will be analyzed using the Statistical Analysis Software (SAS) Version 9.4 or higher, according to the data analysis section (Section 9) of the protocol. This information will also be available in Appendix 16.1.1 of the Clinical Study Report (CSR). Additional important information as appropriate will be given in listings and the CSR. Final study CSR document will include the reports of Main study, mechanistic study and additional analysis.

Unless otherwise specified, the statistical hypothesis tests will be conducted against 1-sided alternative hypothesis, employing a 2.5% level of significance. For other analyses, p-values will be presented as 2-sided, employing a 5% level of significance. Two-sided 95% confidence intervals will be displayed.

Efficacy, safety, and other data will be summarized descriptively as follows:

- for continuous variables, descriptive summary statistics (number of subjects (n), mean, standard deviation (SD), median, minimum, maximum and lower/upper quartiles) for absolute and change (absolute and relative) from Baseline values will be reported by treatment arms (of the Main Study and of the Mechanistic Sub-study, as applicable).
- for categorical variables, frequency (n) and percentage (%) will be presented by treatment arms (of the Main Study and of the Mechanistic Sub-study, as applicable). Percentages will be calculated with respect to the number of evaluable subjects (m) out of the total number of subjects in the analysis set (N) of interest.

For Mechanistic Sub-study at time of final analysis or Week 104 interim analysis (if required) treatment arms are presented by duration of psoriasis for each treatment arm separately as;

New-onset : Arm A1b , Arm A2 and Arm B1b.

Chronic : Arm C1 and Arm C2

Total (wherever required).

In Main Study, after Week 104 subjects continued into the study are low, hence if statistical analysis where missing data is handled using Imputation method then analysis will be performed upto Week 104 unless mentioned otherwise. However, In Mechanistic Sub-study

due to limited number of subjects after Week 104 , listings will be only provided including disposition summary for the final analysis.

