5.6 Statistical models

5.6.1 Primary analysis

For the primary analysis (at Week 52), the following hypothesis testing will be performed:

$$H_{01}: p_{sec} = p_{nbUVB} \text{ versus } H_{A1}: p_{sec} > p_{nbUVB}$$

where p_{sec} and p_{nbUVB} are the proportion of PASI 90 responders in the secukinumab 300 mg s.c. (Arm A1) and nb-UVB (Arm B) groups, respectively.

Model:

Forward selection method will be performed in order to select the subset of significant covariates from Baseline PASI score, age and BMI, and their interaction with treatment.

$\text{Logit}(\pi_i) = \beta_1 * \text{treatment} + \beta_2 * \text{Baseline PASI score} + \beta_3 * \text{age} + \beta_4 * \text{BMI} + \beta_5 * \text{Baseline PASI score} * \text{treatment} + \beta_6 * \text{age} * \text{treatment} + \beta_7 * \text{BMI} * \text{treatment} + \text{error}$

where π_i is the probability that the i th subject is PASI 90 responder given that i th subject receives x_j treatment, where treatment x_j is AIN if j is 1 and nb-UVB if j is 2.

SAS code:

Using the PROC LOGISTIC the estimates of treatment differences and corresponding adjusted odds ratio and 95% CI. For Primary , Additional secondary objective. And in Other section as applicable.

```
proc logistic data= <PASI_IGA> descending covout outest=betas;
  class TRT/param=glm;
  model RESPONDER (event='1')= <Baseline XXX> <Treatment> <Age> <BMI>
    / selection=forward

    details
    lackfit;
  lsmeans trt/diff cl exp ODDSRATIO;
ods output diffs=lsm_diff;
run;
```

If there is any convergence issues, then

For Non convergence, Wald test:

```
PROC FREQ DATA=<Imputed dataset> ORDER=DATA;
  Weight <Count>;
```

```
TABLES <treatment group>*<response variable>/riskdiff(equal var=NULL CI=wald) alpha=0.05;  
RUN;
```

Multiple Imputation

The number of imputations will be set to 500, the seed for the random function will be set to 4572322. The input data set should have one record per subject with Baseline PASI score as well as all change from Baseline PASI score.

To generate the multiple imputed data sets proc MI can be used as follows (example):

```
ODS LISTING CLOSE;  
ODS OUTPUT MissPattern=msgpat VarianceInfo=varinfo ParameterEstimates=param;  
PROC MI DATA=<pasi> OUT=<impdata> SEED=457<studycode> NIMPUTE=500;  
VAR <Baseline BMI> <age>  
    <Baseline PASI>  
    <change from baseline PASI week 16> - <change from baseline PASI week 52> PASI week primary endpoint  
BY <treatment group>;  
RUN;  
ODS LISTING;
```

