- The `ESTIMATE` and `STDERR` in terms of odds ratios from logistic regressions will be transformed to follow a normal distribution before `MIANALYZE` procedure. They will be transformed back to Odds Ratio to get the corrected `ESTIMATE` and corresponding CIs.

An example SAS procedure `MIANALYZE` will be applied as follows:

```
DATA <modified dataset_t>;  
SET <modified dataset>;  
stderr= stderr;  
VARIABLE="estimate";  
RUN ;  
  
ODS LISTING CLOSE;  
ODS OUTPUT ParameterEstimates=<results> VarianceInfo=<varinfo> ModelInfo=<modelinfo>;  
PROC MIANALYZE PARMS=<modified dataset>;  
BY <by-variables>;  
MODELEFFECTS ESTIMATE;  
RUN;  
  
ODS LISTING;  
data <results_back>;  
set <results>;  
estimate=exp(ESTIMATE);  
LCLMEAN=estimate*exp(-1.96*stderr);  
UCLMEAN=estimate*exp(+1.96*stderr);  
RUN ;
```

The ODS OUTPUT data set ParameterEstimates contains the estimate for the log(odds ratio), in ParameterEstimates.Estimates and the lower and upper confidence intervals (ParameterEstimates.LCLmean and ParameterEstimates.UCLmean). These three variables can be back-transformed and will be displayed together with the variable ParameterEstimates.PROBT. For the statistical appendix the ODS OUTPUT data sets Parameter Estimates, VarianceInfo and ModelInfo will be merged and displayed.

Result displayed:

Estimated adjusted odds ratio and the associated 95% confidence interval long with p-value.

In case if logistic regression does not converge, risk difference estimates will be provided. The SAS procedure PROC FREQ for risk difference estimates will be applied as follows:

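### Does halving the logistic p-value for H01 without a stated check on direction undo the 1-sided 2.5% test?

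*SAP*

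**What the plan says.** The primary hypothesis is directional. SAP section 2.5.2 and Protocol section 9.4.2 set the alternative as a higher Week 52 PASI 90 rate on secukinumab (Arm A1) than on nb-UVB (Arm B1). On the level, SAP section 2.5.2 says: "Statistical significance will be evaluated at a 1-sided alpha level of 0.025". The general rule in SAP section 2.1 is that "the statistical hypothesis tests will be conducted against 1-sided alternative hypothesis, employing a 2.5% level of significance".

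The operational step is in the testing strategy of SAP section 2.6.2 and, in the same words, of Protocol section 9.5.1: "The obtained p-value from the fitted logistic regression model will be divided by 2 and this resultant p-value needs to be considered". If the halved value is below 0.025, H01 is rejected, "concluding that there is strong evidence to consider that secukinumab is performing better than nb-UVB at Week 52". If it is above 0.025, H01 is not rejected. The key secondary hypothesis H02 is tested only after H01 is rejected.

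SAP section 2.5.2 also requires the adjusted odds ratio for A1 versus B1 with a 2-sided 95% interval, which it describes as equivalent to a 1-sided 97.5% interval. In the code of SAP section 5.6.1 the treatment contrast is requested with "lsmeans trt/diff cl exp ODDSRATIO". Of the pooled estimate and its limits the SAP says: "These three variables can be back-transformed and will be displayed together with the variable ParameterEstimates.PROBT". If the logistic model does not converge, SAP section 2.5.2 says that "the above hypothesis will be tested using a 1- sided Wald test". Protocol section 9.4.2 says only that "the above hypothesis will be tested using a Wald test", a few lines after setting the 1-sided level.

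**The concern.** A two-sided p-value is small when the effect is large in either direction. Halving it gives the 1-sided p-value for secukinumab superiority only if the odds ratio for A1 versus B1 is above 1. The decision paragraph has two branches, below and above 0.025, and neither looks at the sign of the estimate. The example code prints the pooled p-value without a sign check.

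Taken word for word, a significant result in favour of nb-UVB would fall in the branch that declares secukinumab better. It would also open the gate to H02. The rule would then run at twice its stated level, in the paragraph that is meant to control the familywise error.

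**Working it through.** **Inputs.** From SAP section 3: 80 patients per arm; PASI 90 at Week 52 of 70% in A1 and 35% in B1 before dropout; 20% dropout in B1 counted as non-response, so 0.35 × 0.80 = 28%; stated power 99.9%. From SAP section 2.5.2: 1-sided 0.025. That the model p-value is two-sided is inferred: halving makes sense only if it is, and the code sets no 1-sided option.

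**The plan's own figure.** Difference 0.42, mean rate 0.49.
- Null SE = √(2 × 0.49 × 0.51/80) = 0.0790.
- Alternative SE = √(0.70 × 0.30/80 + 0.28 × 0.72/80) = 0.0717.
- Pooled: (0.42 − 1.96 × 0.0790)/0.0717 ≈ 3.70, power 99.99%.
- Unpooled: 0.42/0.0717 − 1.96 ≈ 3.90, power 99.995%.

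The stated 99.9% is confirmed.

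**What the literal step does.** p/2 < 0.025 is the same event as p < 0.05. Asymptotically it rejects in 5.0% under H01, 2.5% in each direction. Exact enumeration of all 2×2 tables (80 per arm, treatment-only Wald test on the log odds ratio, no covariates, no imputation) gives:

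| Common response rate | Literal step | Step with odds ratio > 1 |
|---|---|---|
| 28% | 4.84% | 2.42% |
| 35% | 5.04% | 2.52% |
| 50% | 4.78% | 2.39% |
| 70% | 4.92% | 2.46% |

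**One wrong-direction table.** Take A1 16/80 and B1 28/80. (28/80 is the 35% before dropout; the rate used for power is 28%, about 22/80, so this is an illustration only.)
- Odds ratio = (16/64)/(28/52) = 0.464.
- SE of the log odds ratio = √(1/16 + 1/64 + 1/28 + 1/52) = 0.365.
- 95% CI 0.227 to 0.949; z = −0.767/0.365 = −2.10; two-sided p = 0.035.
- Halved value 0.018; correct 1-sided p-value 1 − 0.018 = 0.982.

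The literal step would call this a win for secukinumab, beside an interval lying wholly below 1.

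**At the planned rates.** With 70% versus 28%, the same enumeration gives a wrong-direction rejection probability of 1.7 × 10⁻¹⁴. Power is 99.98% with or without the direction condition.

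**If the planning rates were wrong.** With a true 35% in A1 and 50% in B1, a significant result favouring nb-UVB would occur in 47.4% of trials. The planning rates alone therefore do not settle the point; the direction has to be fixed by the rest of the plan.

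**Is it fixed?**
- The sentence just before the halving step, in both documents, says H01 is tested 1-sided at 2.5%. Halving carries out that test; it does not replace it.
- SAP sections 2.1 and 2.5.2 name the 1-sided alternative and its direction.
- The contrast is oriented in advance: odds ratio for A1 versus B1, with the data sorted so that nb-UVB comes last (SAP section 5.6.1).
- The code forms the lower limit as the odds ratio times exp(−1.96 × SE). It exceeds 1 exactly when log odds ratio/SE > 1.96, which is the 1-sided 2.5% test in the right direction. Apart from the reference distribution behind the printed p-value, the required interval already contains the check.

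**The case for a change.** The best case for a change is that a rule written out step by step should deliver the level it names, above all where it controls the familywise error and opens H02. The odds ratio and its interval are required outputs, but no sentence makes them part of the rejection rule. The SAP expressly calls the non-convergence fallback 1-sided, so the main route is the less exactly described of the two. A short clause would close the gap at no cost in data or power.

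The omission is real and stands in both documents, and the arithmetic of the literal reading is correct. The harm does not follow. It needs someone to ignore the hypothesis named in the preceding sentence and to report superiority of secukinumab next to an odds ratio significantly below 1. The absence of a sign check in the code says little, because that code is offered as an example for display. New wording would also come too late to govern the test: SAP section 2.14.1 records that a study report was already prepared for the Week 52 primary analysis. A report line confirming the direction would only repeat what the required odds ratio and interval show.

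**Conclusion.** No change is needed. The halving sentence leaves out a condition that the stated alternative, the 1-sided 2.5% level and the required A1 versus B1 interval all supply. Read with them, the test runs at about 2.5% (2.4–2.5% in the unadjusted enumeration) with the stated power. The 4.8–5.0% figure belongs only to a reading that cuts the sentence off from the hypothesis it implements.

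This rests on the model p-value being two-sided and on analysts applying the written alternative. The enumeration leaves out covariate selection and multiple imputation; neither affects the argument about direction. The point concerns H01 alone, since the plan does not say that the H02 p-value is obtained by halving. If either document were reopened for another reason, a clause on direction would be harmless tidying, but no result or conclusion depends on it.
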